**12.4. Statistical Methods**

Tabular summaries of data will be descriptive in nature (i.e., number of patients [n], mean, standard deviation, median, minimum and maximum for continuous variables and n and percent for categorical variables). For efficacy parameters, including objective response rate and disease control rate, 95% confidence intervals will be presented using the Wilson's score method.

Protocol deviations will be listed. Protocol deviations that might substantially affect efficacy analyses will be determined prior to database lock.

A more detailed description of analysis methods will be provided in the SAP to be completed prior to the clinical database lock.

**13. SAFETY**

Adverse events observed, mentioned on open questioning by a member of the Investigator team or spontaneously reported by the subject will be documented. Adverse events will be documented event based. The observation phase for adverse events will start with signing the informed consent and will end at the completion of the active reporting period. Planned timepoints for all safety assessments are provided in the Study Assessments ([Section 10](#)). Unscheduled safety measurements may be obtained at any time during the study to assess any perceived safety issues.

**13.1. Definition of Adverse Events****13.1.1. Adverse Event**

An adverse event is any untoward medical occurrence or the worsening of a pre-existing medical condition following or during exposure to a pharmaceutical product, whether or not considered causally related to the product. Development of new disease lesions or disease progression is not considered an adverse event.

All AEs and SAEs occurring in a patient during the active collection period as described in [Section 13.5.3](#). will be recorded on the appropriate CRF from the signature of the informed consent. All SAEs must be reported on the CT SAE Report Form to Pfizer Safety immediately upon awareness and under no circumstance should this exceed 24 hours. A worsening of a condition/disease recorded in the medical history is reportable as an AE. Documentation must be supported by an entry in the patient's source medical records. Laboratory abnormalities requiring treatment or considered by the investigator to be clinically relevant should be reported in the CRF as an AE. Each AE is to be evaluated for duration, severity and causal relationship with the IP.

For the purposes of this study, events that are unequivocally due to disease progression should not be reported as AEs unless the outcome is fatal within the active collection period. Hospitalization due to signs and symptoms of disease progression should not be reported as an SAE. If the malignancy has a fatal outcome during the study, the event leading to death must be recorded as an AE on the CRF, and as an SAE with CTCAE Grade 5 if it occurs during the active collection period. Symptoms of the disease under study/lack of efficacy should not be classified as AEs as long as they are within normal day-to-day fluctuations or expected progression of the disease.

The development of a new cancer should be regarded as an AE and will generally meet at least one of the SAE criteria. New cancers are those that are not the primary reason for study treatment and have been identified after the patient's inclusion in this study. They do not include metastases of the original cancer.

**13.1.2. Serious Adverse Event**

A serious adverse event is an adverse event occurring during any study at any dose of the investigational product(s) that fulfills one or more of the following:

- Results in death

- Is immediately life-threatening (the subject was at risk of death at the time of the event; this does not refer to an event which hypothetically might have caused death if it were more severe)
- Requires in-patient hospitalization or prolongation of existing hospitalization
- Results in persistent or significant disability or incapacity
- Results in a congenital abnormality or birth defect
- Is an important medical event that may jeopardize the patient or may require medical intervention to prevent one of the outcomes listed above

Medical or scientific judgment should be exercised in deciding whether reporting is appropriate in other situations, such as important medical events that may not be immediately life threatening or result in death or hospitalization but may jeopardize the patient or may require medical or surgical intervention to prevent one of the other outcomes listed in the above definition. These should also be considered serious.

Examples of such events include invasive or malignant cancers, intensive treatment in an emergency room or at home for allergic bronchospasm, blood dyscrasias or convulsions that do not result in hospitalization, or development of drug dependency or drug abuse.

All serious adverse events that occur after any patient has signed informed consent, been enrolled, before treatment, during treatment, or within 30 days following the cessation of treatment, whether or not they are related to the study intervention, must be recorded on a Serious Adverse Event form.

### **13.2. Clarifications to Serious Adverse Event Reporting**

- Death is an outcome of a serious adverse event and not a serious adverse event in itself. When death is an outcome, report the event(s) resulting in death as the serious adverse event term (e.g., “pulmonary embolism”). If the cause of death is unknown, report “Death, unknown cause” as the serious adverse event term.
- Pre-planned or elective hospitalizations including social and/or convenience situations (e.g., respite care) are excluded from serious adverse event reporting. In addition, emergency room visits and admission under 23-hour observation are excluded from serious adverse event reporting; however, such events should still be reported on the appropriate adverse event eCRF page.
- An isolated laboratory abnormality is not reportable as a serious adverse event unless the Investigator assesses that the event meets the standard ICH criteria for a serious adverse event.

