### **13.5.6. Notification**

#### **Serious Adverse Events**

The investigator or designee must report all SAEs (related and unrelated) promptly to Pfizer Safety within 24 hours of the knowledge of the occurrence.

To report the SAE, complete the CT SAE form electronically in the Pfizer SAE Submission Assistant (PSSA) tool. When the form is completed, Pfizer Safety personnel will be notified electronically. If the event meets serious criteria and it is not possible to access the PSSA tool, then fax the completed paper CT SAE form to Pfizer Safety within 24 hours of awareness. When the PSSA tool becomes available, the SAE information must be entered within 24 hours of the PSSA system becoming available.

At the time of first notification, the investigator or designee should provide the following information, if available:

- Protocol number
- Reporter (study site and investigator)
- Patient's study number
- Patient's year of birth
- Patient's gender
- Date of first dose of IP(s)

- Date of last dose of IP(s), if applicable
- AE term
- Date of occurrence of the event
- A brief description of the event, outcome to date, and any actions taken
- The seriousness criteria(on) that were met
- Concomitant medication at onset of the event
- Relevant medical history information
- Relevant laboratory test findings
- Investigator's opinion of the relationship to IP(s). ("Is there a reasonable possibility that the IP caused the SAE? Yes or No?")

It should be noted that the CT SAE Report Form for reporting of SAE information is not the same as the AE page of the CRF. When the same data are collected, the forms must be completed in a consistent manner. AEs should be recorded using concise medical terminology and the same AE term should be used on both the CRF and the CT SAE Report Form for reporting of SAE information.

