### **13.5.8. Adverse Events of Special Interest**

The following events are considered AEs of special interest based on preclinical toxicology studies with TTI-621. Additional details are provided in the current version of the IB for TTI-621.

- Infusion-related reaction
- Thrombocytopenia
- Hemorrhage
- Anemia

AESIs are examined as part of routine safety data review procedures throughout the clinical trial and as part of signal detection processes. Should an aggregate analysis indicate that these pre-specified events

occur more frequently than expected, e.g., based on epidemiological data, literature or other data, then this will be submitted and reported in accordance with Pfizer's safety reporting requirements. Aggregate analyses of safety data will be performed on a regular basis per internal SOPs.

All AESIs must be reported as an AE or SAE following the procedures described in [Sections 13.5.4](#) and [13.5.6](#). An AESI is to be recorded as an AE or SAE on the CRF. In addition, an AESI that is also an SAE must be reported using the CT SAE Report Form.

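### Section 13.2 takes emergency room visits and 23-hour observation out of SAE reporting without the proviso that any other seriousness criterion still applies, which conflicts with 13.1.2

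*Protocol*

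**What the plan says.** Protocol Section 13.1.2 defines an event as serious if it meets any one of its listed criteria. In-patient hospitalization is one; immediate threat to life and important medical event are others. Of important medical events that do not lead to hospitalization it says: "These should also be considered serious". Among its examples is "intensive treatment in an emergency room or at home for allergic bronchospasm, blood dyscrasias or convulsions that do not result in hospitalization".

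Section 13.2, which is meant to clarify SAE reporting, has a bullet that first removes pre-planned and elective hospitalizations and then adds that "emergency room visits and admission under 23-hour observation are excluded from serious adverse event reporting". It continues that "such events should still be reported on the appropriate adverse event eCRF page". The bullet stops there. The next bullet, on isolated laboratory abnormalities, also excludes a class of findings, but only "unless the Investigator assesses that the event meets the standard ICH criteria for a serious adverse event".

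On timing, Section 13.5.6 states: "The investigator or designee must report all SAEs (related and unrelated) promptly to Pfizer Safety within 24 hours of the knowledge of the occurrence". Section 13.1.1 sets the same limit. Section 13.5.8 names infusion-related reaction, thrombocytopenia, hemorrhage and anemia as AESIs. It gives them no fast route of their own: "an AESI that is also an SAE must be reported using the CT SAE Report Form".

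**The concern.** Taken at its word, the bullet decides SAE status by where the patient was treated. Section 13.1.2 decides it by the medical importance of the event. For an event treated in an emergency room and not admitted, the two can give different answers, and a section offered as clarification is one that a site may reasonably treat as controlling.

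The events most exposed belong to this drug's known toxicities. The note to Table 11 says that acute infusion reactions usually settle within a day of the infusion. Section 3.8.1 says that platelet falls mostly came in the first 24 hours and usually recovered within a week. Short-stay care is therefore plausible. Safety is a primary objective, and the safety profile is a primary endpoint for dose escalation and a secondary endpoint for expansion. At stake are the timeliness of SAE reports and the comparability of serious-event counts between sites.

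**Working it through.** The protocol states no figure to reproduce here. The check is to apply both rules to the same cases and then follow each result through the reporting chain.

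**Step 1. The two rules on the same event.**

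| Event | 13.1.2 | 13.2, read literally | Agree? |
|---|---|---|---|
| Allergic bronchospasm after TTI-621, intensively treated in the emergency room, not hospitalized | Serious (a named example) | Outside SAE reporting; AE eCRF page | No |
| Bleeding or symptomatic thrombocytopenia managed under 23-hour observation | Serious if life-threatening or an important medical event | Outside SAE reporting; AE eCRF page | No, if a criterion is met |
| Isolated low platelet count | Serious if a criterion is met | Laboratory bullet, with its override | Yes |
| Reaction leading to in-patient admission | Serious | Not excluded | Yes |

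The conflict is confined to the first two rows. The override in the laboratory bullet shows that the authors had such a proviso available and did not attach it to the emergency room and observation bullet.

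**Step 2. The reporting clock.** An SAE must reach the sponsor's safety group within 24 hours (13.1.1, 13.5.6). An event handled only as an AE reaches the sponsor through the eCRF, where entry is expected in about two weeks (14.7). AESI status does not shorten this, because the SAE form is required only when the AESI is also an SAE (13.5.8).

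**Step 3. The SAP tables.** SAP Section 9.3 tabulates Serious TEAEs and treatment-related Serious TEAEs. SAP Section 6.2 takes the reported data from the eCRF. Protocol Section 13.5.4 requires serious and non-serious events alike in the CRF, with seriousness recorded. There are then two cases:
- SAE form not sent, event marked serious on the eCRF: the report is late or missing, but the event can still be counted as serious.
- SAE form not sent, event marked non-serious on the eCRF: the report is missing and the event drops out of the Serious TEAE counts.

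**Step 4. Which events lead.** Protocol Section 3.5.2.1.2 and Table 3 give, for TTI-621-01 (N = 235), 22 subjects with a treatment-related SAE, 7 with infusion-related reaction and 4 with thrombocytopenia.
- Any: 22/235 = 9.4% (table: 9%).
- Infusion-related reaction: 7/235 = 3.0% (table: 3%).
- Thrombocytopenia: 4/235 = 1.7% (table: 2%).

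These are the two most frequent treatment-related SAEs. The figures show which event types the conflict touches, not how many reports would be affected.

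**The case against.** The best defence is that the bullet concerns only the hospitalization criterion. It opens with elective admissions, and what it lists are kinds of encounter, not diagnoses or outcomes. On that reading an emergency room visit or observation stay simply does not count as in-patient hospitalization, 13.1.2 governs everything else, and there is no conflict. This may well be the intent. It is not what the sentence says: the exclusion is from SAE reporting as a whole.

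There are also backstops. The sponsor reports as an SAE any non-serious AE that it determines to be serious (13.5.4). The Medical Monitor reviews all adverse events on an ongoing basis (13.7). Safety calls are weekly in escalation and start at two-week intervals in expansion (13.8). This stands as far as it goes: such events may be found later, but none of these checks is tied to the 24-hour limit.

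A reader might infer more than the documents support, in three ways:
- That these events are bound to go unreported. An investigator who gives 13.1.2 priority would report them correctly.
- That they are necessarily missing from the Serious TEAE tables. The AE eCRF page records seriousness, so this happens only when the event is also marked non-serious there.
- That every low platelet count is affected. Isolated laboratory findings keep their own override.

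**Conclusion.** The concern holds as a conflict between adjacent sections. Section 13.2 lacks a proviso that 13.1.2 requires, and literal use of 13.2 can keep an event off the 24-hour SAE route. The consequence is possible delay and inconsistent classification between sites. Under-counting of Serious TEAEs follows only where the eCRF entry is also non-serious.

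Its size cannot be stated. A reader might apply the TTI-621-01 rates to about 80 patients and assume some share treated in the emergency room or under observation. The documents give no such share. The rates also come from weekly dosing, mostly in hematologic malignancies, with antihistamine and acetaminophen premedication, whereas this trial adds doxorubicin and a steroid (Sections 3.5.2.1, 3.8.1 and Table 6). Infusions are given where emergency facilities and trained staff are present (8.3), so some reactions may never reach an emergency room.

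The conclusion rests on the wording alone. It assumes only that some sites will take 13.2 at face value.

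**What to change.** Reword the bullet in 13.2 along these lines: *An emergency room visit or an observation stay of under 24 hours does not by itself meet the hospitalization criterion; the event remains an SAE, with 24-hour reporting, if it meets any other criterion in 13.1.2, including life-threatening or important medical event.* A protocol amendment or a letter to sites would carry it.

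Before database lock, query AESIs entered as non-serious that involved emergency room care or observation, and have the investigator reassess seriousness against 13.1.2. SAP Section 4.3.2 describes Cohort B Stage 1 and Cohort C enrollment in the past tense, so this query may matter more than the new wording. Under 13.2 the events should already be on the AE eCRF page.

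The cost is one sentence, one targeted query and a few more SAE reports. Nothing changes in treatment, sample size or analysis method.

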### **13.3. Assessment of Causality**

The relationship of each adverse event to administration of the study drug(s) will be assessed by the Investigator after careful consideration of all relevant factors such as (but not limited to) the underlying study indication, co-existing disease, concomitant medication, relevant history, pattern of the adverse event, temporal relationship to receipt of the study medication(s) and de-challenge or re-challenge.

Study drug or study treatment refers to intravenously-administered doxorubicin and intravenously-administered TTI-621. The assessment of relationship to study drug or study treatment will be done for

each drug separately. If the Investigator feels such a distinction cannot be made, the assessment will be based on the combination of the two drugs.

The assessment of causality is based on the question of whether there was a reasonable causal relationship to the study drug in question according to the following guidelines:

**RELATED** (possible, probably or definitely related): there is a reasonable possibility that the study treatment caused the event; one or more of the following criteria apply:

- The event follows a reasonable temporal sequence from administration of study treatment
- The event could not be reasonably attributed to the known characteristics of the patient's clinical state, environment or toxic factors or other modes of therapy administered to the patient
- The event follows a known pattern of response to study treatment
- The event disappears or decreases on cessation or reduction in dose of the study treatment. In some situations, an AE will not disappear or decrease in intensity upon discontinuation of the study treatment despite other clear indications of relatedness

**UNRELATED** (unlikely related or definitely not related): There is no reasonable possibility that the study treatment caused the event; one or more of the following criteria apply:

- The event does not follow a reasonable temporal sequence from administration of study treatment
- The event could be reasonably attributed to known characteristics of the patient's clinical state, concurrent illness, environment or toxic factor or other therapies administered to the patient
- The event does not follow a known pattern of response to study treatment
- The event does not disappear or decrease on cessation or reduction in dose of the study treatment, and it does not reappear or worsen when the study treatment is re-administered
- There is a clear alternative explanation

#### **13.4. Assessment of Severity**

The severity rating of an adverse event refers to its intensity. The severity of each adverse event will be categorized using the NCI CTCAE v5. For any term that is not specifically listed in the CTCAE scale, intensity should be assigned a grade of 1 through 5 using the following CTCAE guidelines:

Grade 1: Mild; asymptomatic or mild symptoms; clinical or diagnostic observations only; intervention not indicated

Grade 2: Moderate; minimal, local or noninvasive intervention indicated; limiting age-appropriate instrumental activities of daily living

Grade 3: Severe or medically significant but not immediately life-threatening; hospitalization or prolongation of hospitalization indicated; disabling; limiting self-care activities of daily living

Grade 4: Life-threatening consequences; urgent intervention indicated

Grade 5: Death related to adverse event

It is important to distinguish between serious adverse events and severe adverse events. Severity is a measure of intensity whereas seriousness is defined by the criteria under [Section 13.1.2](#). An adverse event of severe intensity may not be considered a serious adverse event.

### 13.5. Action Taken

Any action with study treatment to resolve the adverse event is to be documented using the categories listed below. The study drug action should be recorded separately for each component as detailed in the eCRF.

- Drug withdrawn
- Drug interrupted
- Dose reduced
- Dose not changed
- Not applicable
- Unknown

#### 13.5.1. Other Specific Treatments of Adverse Event

- None
- Remedial drug therapy
- Other

#### 13.5.2. Outcome of Adverse Event

The outcome of the AE is to be documented as follows:

- Recovered / resolved
- Recovering / resolving
- Recovered / resolved with sequelae
- Not recovered / not resolved
- Fatal
- Unknown

#### 13.5.3. Time Period and Frequency for Collecting AE and SAE Information

The time period for actively eliciting and collecting AEs and SAEs (“active collection period”) for each patient begins from the time the patient provides informed-consent, which is obtained before undergoing any study-related procedure and/or receiving study intervention, through and including a minimum of 30 calendar days after the last administration of the study intervention.

For patients who are screen failures, the active collection period ends when screen failure status is determined.

If the patient withdraws from the study and also withdraws consent for the collection of future information, the active collection period ends when consent is withdrawn.

If a patient permanently discontinues or temporarily discontinues study intervention because of an AE or SAE, the AE or SAE must be recorded on the CRF and the SAE reported using the CT SAE Report Form.

Investigators are not obligated to actively seek information on AEs or SAEs after the patient has concluded study participation. However, if the investigator learns of any SAE, including a death, at any time after a patient has completed the study, and they consider the event to be reasonably related to

the study intervention, the investigator must promptly report the SAE to Pfizer using the CT SAE Report Form.

#### **13.5.4. Documentation**

All AEs (serious and non-serious) occurring within the period of observation for the study must be documented in the CRF with the following information, where appropriate. (The period of observation for the study is described in [Section 13.5.3](#)).

- AE name or term
- When the AE first occurred (start date)
- When the AE stopped (stop date or an indication of “ongoing”)
- Severity of the AE
- Seriousness (hospitalization, death, etc.)
- Actions taken
- Outcome
- Investigator opinion regarding the AE relationship to the IP(s)

All nonserious AEs and SAEs occurring in a patient during the active collection period which begins after obtaining informed consent as described in [Section 13.5.3](#), will be recorded on the AE section of the CRF.

The investigator or designee is to record on the CRF all directly observed and all spontaneously reported AEs and SAEs reported by the patient.

The investigator must record his or her reasoning for this decision in the patient’s medical record and as a comment on the CRF

Reporting of AEs and SAEs for patients who fail screening are subject to the CRF requirements as described in [Section 13.5.3](#).

As part of ongoing safety reviews conducted by the sponsor, any nonserious AE that is determined by the sponsor to be serious will be reported by the sponsor as an SAE. To assist in the determination of case seriousness, further information may be requested from the investigator to provide clarity and understanding of the event in the context of the clinical study.

If a patient begins a new anti-cancer therapy, the recording period for nonserious AEs ends at the time the new treatment is started; however, SAEs must continue to be recorded on the CRF during the above indicated active collection period. Note that a switch to a commercially available version of the study intervention is considered as a new anti-cancer therapy for the purposes of SAE reporting.

